9.3.4. Adverse Event Relationship to Study Drug

The relationship of an AE to the study drug should be based on the judgment of the investigator and assessed using the following guidelines:

- **Related:** Previously known toxicity of agent; or an event that follows a reasonable temporal sequence from administration of the drug; that follows a known or expected response pattern to the suspected drug; that is confirmed by stopping or reducing the dosage of the drug; and that is not explained by any other reasonable hypothesis.
- **Probably related:** An event that follows a reasonable temporal sequence from administration of the drug; that follows a known or expected response pattern to the suspected drug; that is confirmed by stopping or reducing the dosage of the drug; and that is unlikely to be explained by the known characteristics of the participant's clinical state or by other interventions.
- **Possibly related:** An event that follows a reasonable temporal sequence from administration of the drug; that follows a known or expected response pattern to that suspected drug; but that could readily have been produced by a number of other factors.
- **Unrelated:** An event that can be determined with certainty to have no relationship to the study drug.

9.3.5. Serious Adverse Event Definition and Reporting Procedures

Any AE that meets the definition of serious noted below and occurs in a participant during the course of the study must be reported to the sponsor by telephone within 24 hours of the investigator becoming aware of the event. In addition, a serious adverse event form (SAE) must be completed by the investigator or designee and faxed to the study sponsor within 24 hours of the investigator becoming aware of the event. In addition, the site investigator or designee must report SAEs to their local Ethics Committee (EC) in accordance with the EC's standard operating procedures and policies.

An SAE is defined as an adverse event that suggests a significant hazard or side effect, regardless of the relationship to study drug. An SAE includes, but may not be limited to, any event that:

- Results in death.
- Is life-threatening. This definition implies that the participant, in the view of the investigator, is at immediate risk of death from the event. It does not include an event that, had it occurred in a more serious form, might have caused death.
- Requires inpatient hospitalization or prolongs existing hospitalization.
- Results in persistent or significant disability/incapacity.

- Results in a congenital anomaly or birth defect. This serious criterion applies if a participant exposed to an investigational product gives birth to a child with a congenital anomaly or birth defect.

Medical and scientific judgment will be exercised in deciding whether classification of an AE as serious is appropriate in other situations, such as important medical events that may not be immediately life-threatening or result in death or hospitalization but may jeopardize the participant or require intervention to prevent one of the outcomes listed in the definition above. These should also usually be considered serious. Examples of such events include allergic bronchospasm requiring intensive treatment in an emergency room or at home, blood dyscrasias or convulsions that do not result in inpatient hospitalization, or the development of drug dependence or abuse.

Serious adverse events occurring after a participant is discontinued from the study will only be reported if the investigator believes that the event may have been caused by the study drug or a protocol procedure.

For the purpose of expedited reporting to regulatory agencies, an investigator will be responsible for identifying any adverse event that is serious, unexpected, and believed to be related to study drug. An adverse event or suspected adverse reaction is considered “unexpected” if it is not consistent with the risk information described in the Investigator’s Brochure. For example, under this definition, hepatic necrosis would be unexpected (by virtue of greater severity) if the investigator brochure or investigational drug application referred only to elevated hepatic enzymes or hepatitis. Similarly, cerebral thromboembolism and cerebral vasculitis would be unexpected (by virtue of greater specificity) if the investigator brochure or investigational drug application listed only “cerebral vascular accidents.

9.4. Safety Monitoring

A medically qualified person will monitor blinded safety data throughout the study. The sponsor (or designee) will review SAEs within time frames mandated by regulatory requirements and will review trends and adverse events at periodic intervals.

A Safety Monitoring Committee (SMC) comprising 3 members will review safety and available PK data prior to dose escalation to the next dose cohort in Parts 1 and 2, as well as between the fasted and fed periods in Part 1, Cohort C. The SMC will be composed of the independent medical monitor, principal investigator, and sponsor’s medical representative. Other members of the investigational team may join the SMC as non-voting attendees as deemed appropriate. Before dose escalation in the single-ascending dose and multiple-ascending dose cohorts, the SMC will review all available safety and tolerability data for a minimum of 7 participants who have completed the planned safety assessments up to 48 hours after dosing to ensure that at least 5 participants received active study drug. The

following data are required for interim study decisions: adverse events, vital signs, safety laboratory values, and ECGs

Dose escalation will not occur with any of the following:

- a serious adverse reaction (i.e., a serious adverse event considered at least possibly related to the active drug) in one subject.
- Grade 3 or higher nonserious adverse reactions (i.e., severe nonserious adverse event considered related to the active drug administration) in two participants in the same cohort, independent of whether they occurred within the same system organ class.

The data will be reviewed blinded unless the SMC considers it necessary to unblind the data for safety concerns. Before breaking the code (per standard procedures), the potential decisions and actions will be determined.

SMC decisions on dose escalation will be taken in consensus between the SMC members. If consensus cannot be reached, the principal investigator, who has the ultimate responsibility for the safety of participants, will make the final decision on whether to continue or stop the study. The SMC's decisions and their rationale will be documented.

10. QUALITY CONTROL AND QUALITY ASSURANCE

The investigator agrees to be responsible for implementing and maintaining quality control and quality assurance systems to ensure that trials are conducted and data are generated, documented, and reported in compliance with the protocol, accepted standards of Good Clinical Practice, and all applicable federal, state, and local laws, rules and regulations relating to the conduct of the clinical study.

The investigator also agrees to conduct the study in an efficient and diligent manner and in conformance with this protocol; generally accepted standard of Good Clinical Practice; and all applicable federal, state, and local laws, rules, and regulations relating to the conduct of the clinical study.

The investigator must allow study-related monitoring, audits, and inspection by the EC, sponsor (or designee), government regulatory agencies, and, if applicable, University compliance and quality assurance groups of all trial-related documents and procedures.

The investigator shall prepare and maintain accurate study documentation in compliance with Good Clinical Practice standards and applicable federal, state, and local laws, rules, and regulations.

11. DATA ANALYSIS METHODS

11.1. Determination of Sample Size

No formal sample size calculation was done. Based on experience from previous similar studies, the target number of participants to be enrolled is appropriate for the assessment of safety and tolerability.

11.2. Statistical and Analytical Plans

11.2.1. General Considerations

The analysis of safety variables will include all participants who receive study drug, including participants in the additional 400 mg food-effect cohort (Cohort 1C-2).

All variables will be summarized by descriptive statistics for each treatment group. The statistics for continuous variables will include mean, median, standard deviation, and number of observations. Categorical variables will be tabulated using frequencies and percentages. Where confidence intervals are presented, they will be two-sided 95% confidence intervals.

11.2.2. Handling of Missing Data

Missing data will not be imputed for safety analyses.

11.2.3. Participant Disposition

Study participant disposition will be summarized by treatment group. Participants who discontinued study drug prematurely or withdrew from the study will be summarized and listed, with reason for early termination/withdrawal.

11.2.4. Participant Characteristics

Demographic and other baseline characteristics will be summarized by treatment group.

11.2.5. Treatment Compliance

As all study drug dosing is administered at the clinical unit, treatment compliance will be evaluated based on the dosing data recorded by the study personnel.

11.2.6. Pharmacokinetic Analyses

The following PK parameters will be estimated from serial plasma CC-42344 concentration data using noncompartmental analysis.

Single Dose: maximum plasma concentration (C_{\max}) and time to C_{\max} (T_{\max}), the elimination rate constant (λ_z) and half-life ($t_{1/2}$), area under the curve (AUC) to the last time with a concentration \geq lower limit of quantitation (LLOQ) [$AUC_{(0-t)}$] and to infinity [$AUC_{(inf)}$].

Multiple Dose: C_{\max} , T_{\max} , AUC over the 24-hour dosing interval [$AUC_{(0-24)}$] on Days 1 and 14, and the elimination rate constant (λ_z) and half-life ($t_{1/2}$) after the last dose on Day 14.

All analyses will be done using the actual elapsed sampling times. Plasma concentrations and PK parameters will be summarized using descriptive statistics.

The PK parameters C_{\max} , $AUC_{(0-t)}$, and $AUC_{(\text{inf})}$ will be compared between the fed and fasted cohorts using an analysis of variance (ANOVA) model with treatment as a fixed effect and subject as a random effect. The geometric mean ratios and associated 90% confidence intervals will be estimated from the statistical model and used to assess the effect of food.

The attainment of steady-state for each dose level in the multiple-ascending dose phase will be assessed by a comparison of the predose plasma concentrations obtained as indicated in the Schedule of Events (see Sections 2.3 and 2.4) using an ANOVA model with day as a fixed effect and subject as a random effect. Paired comparisons will be done to determine when steady-state has been reached.

Pharmacokinetic parameters will be compared among doses in the single-ascending dose and multiple-ascending dose phases and between phases using descriptive statistics and graphical displays. Relationships between C_{\max} and the AUCs and dose for both phases will be assessed using the power model:

$$P = a \times \text{Dose}^b$$

where P represents the parameter and a and b are constants. A value of b of ~ 1 with a 95% confidence interval that includes 1 indicates linearity or dose proportionality. The power model will be fit to the individual subject data using nonlinear least squares regression, i.e., SAS PROC NLIN or equivalent.

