14. Acute illness (gastrointestinal, infection [e.g., influenza] or known inflammatory process) at screening or Day -1.
15. Abnormal screening ECG, including QT intervals corrected with Fridericia's formula > 450 msec for males or > 470 msec for females, or participant has any cardiac rhythm other than sinus rhythm that is interpreted by the investigator to be clinically significant.
16. Supine resting bradycardia (pulse heart rate [HR] < 40 bpm) or a supine resting tachycardia (HR > 100 bpm) during vital sign measurements at screening or Day -1. Vital sign measurements may be repeated at the investigator's discretion.

17. Hypertension, defined as a supine resting systolic blood pressure >140 mm Hg or a supine resting diastolic blood pressure >90 mm Hg during vital sign measurements at screening or Day -1. Vital sign measurements may be repeated at the investigator's discretion.
18. Hypotension, defined as a supine resting systolic blood pressure <90 mm Hg or a supine resting diastolic blood pressure <40 mm Hg during vital sign measurements at screening or Day -1. Vital sign measurements may be repeated at the investigator's discretion.
19. Known personal or family history of congenital long QT syndrome or known family history of sudden death.
20. Has donated blood or plasma within 30 days prior to screening or had a loss of whole blood of more than 500 mL within the 30 days prior to screening, or receipt of a blood transfusion within one year prior to screening.
21. Taking, or have taken, any prescribed medication in the 14 days before dosing or over-the-counter drug, including herbal remedies, in the 7 days before dosing. Exceptions are vitamins, minerals, paracetamol, hormone replacement therapy, and hormonal contraception. Additional exceptions may apply on a case-by-case basis if considered not to interfere with the objectives of the study, as agreed by the principal investigator and sponsor's medical monitor.
22. Failure to satisfy the investigator of fitness to participate for any other reason.

Investigational Drug

CC-42344

Study Drug Doses and Route of Administration

CC-42344 or placebo given orally. Study drug will be provided in capsule form. Part 1 will include single-ascending doses of CC-42344 100 mg, 200 mg, 400 mg, and 800 mg. The 400-mg food-effect cohort will receive a second dose on Day 9. Part 2 will include multiple doses of CC-42344 50 mg, 100 mg, and 200 mg once daily (QD) for 14 days, and 400 mg QD and 400 mg BID for 5 days.

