- 6 Only for women of postmenopausal status.
- 7 Serology screening will include tests for hepatitis B surface antigen, hepatitis C virus, and human immunodeficiency virus.
- 8 Standard clinical safety labs will be collected non-fasted.
- 9 PK samples to be collected before dosing (within 30 minutes) and at 0.25, 0.5, 0.75, 1, 1.5, 2, 2.5, 3, 3.5, 4, 6, 8, 12, 24, 36, and 48 h after dosing. Additional samples to be collected at 72 and 96 hours postdose for Cohorts 1C and 1D. Sampling windows are \pm 5 minutes for samples through 4 h postdose, \pm 10 minutes for samples at 6 and 8 h, \pm 30 minutes for samples from 12 to 48 h, and \pm 4 h for samples at 72 and 96 h. When ECGs and vital signs are scheduled at the same time as PK samples, the sample will be taken at the scheduled time point, with the ECGs and vital signs obtained as close as possible prior to the blood draw.
- 10 End of study visit for all cohorts except for the food-effect cohort, Cohort 1C. See Section 2.2 for schedule of events for days 8-16 for Cohort 1C.
- 11 Alcohol breath testing may be replaced with a question asking that participants confirm that they have refrained from any alcohol intake for the time period outlined in the protocol

2.2. Part 1 Cohort 1C Schedule of Events – Period 2

	Clinical Unit						EOS Visit ⁹
	Day 8	Day 9			Day 10	Day 11	Day 16
Assessments		Pre-dose	Dosing	Post-dose			(+/-1 d)
Unit Check-in	X						
Informed consent							
Inclusion/exclusion criteria	X	X					
Demographic data							
Medical history							
Prior medication history							
Vein assessment							
Physical examination ¹	X			X (abbrev)		X (abbrev)	X (abbrev)
Height							
Weight	X						
12-lead ECG ²	X	X		X	X	X	X
Vital signs ³	X	X		X	X	X	X
High-fat breakfast ⁴		X					
Study Drug			X				
Adverse event reporting ⁵	X	X	X	X	X	X	X
Concomitant medications	X	X			X	X	X
Alcohol breath test ¹⁰	X						
Drugs of abuse screen	X						
Pregnancy screen ⁶	X						X
Clinical Safety Labs ⁷	X			X	X		X
Plasma CC-42344 levels ⁸		X		X	X	X	
Discharge from Unit						X	

Footnotes

Note: The washout window between Period 1 and Period 2 may be optionally extended for up to 3 days, with other Period 2 visits adjusted accordingly. Thus, dosing for Period 2 may occur between Day 9 and Day 12.

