6. INVESTIGATIONAL PLAN

6.1. Summary of Study Design

This is a single-center, randomized, double-blind, placebo-controlled phase 1 study of the influenza A virus replication inhibitor CC-42344 given orally to healthy participants at a single site in Australia. Participants will be recruited by Linear Clinical Research Ltd. Screening assessments must be done to determine participant eligibility. Written consent must be obtained before conducting any study procedures.

Part 1: Single-Ascending Dose

Participants will be randomly assigned within each cohort to receive a single dose of CC-42344 or placebo. Doses will escalate in sequential dose cohorts. It is planned that 4 cohorts will be dosed with 8 healthy participants per cohort (6 active and 2 placebo in each cohort). Each cohort in Part 1 will include the initial dosing of a sentinel group (1 CC-42344 and 1 placebo) at least 24 hours before dosing the remaining 6 subjects in the cohort (5 CC-42344 and 1 placebo). The remainder of the cohort will only be dosed if, in the opinion of the investigator, there is no significant safety concern identified in the sentinel subjects within the first 24 hours after administration of the dose (CC-42344 or placebo). The following regimens are planned:

- Cohort 1A (N=8): 100 mg CC-42344 or placebo.
- Cohort 1B (N=8): 200 mg CC-42344 or placebo.
- Cohort 1C (N=8): 400 mg CC-42344 or placebo on Days 1 and 9 (food effect).
- Cohort 1D (N=8): 800 mg CC-42344 or placebo.

Cohort 1C will be a two-period sequential food-effect cohort in which participants will receive a single dose of study drug under fasted conditions on Day 1 and a single dose of study drug under fed conditions on Day 9.

After the study was conducted, it was found that the Cohort 1C PK data were not interpretable due to issues with the execution of the assay for plasma CC 42344 levels at the contracted laboratory. Therefore, an additional cohort (Cohort 1C-2) will be enrolled to generate the 400 mg PK and food-effect data. This cohort will comprise 6 participants, all of whom will receive a single 400-mg dose of open-label CC-42344 on Day 1 under fasted conditions and a single 400-mg dose of open-label CC-42344 on Day 9 under fed conditions. The study entry criteria, activities, and assessments will be the same as those described for the main study.

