7.2.3. Participant Replacement

In both Parts 1 and 2, up to 2 replacement participants may be enrolled per cohort. An exception is participants withdrawn due to an adverse event related to CC-42344, who will be considered evaluable and will not be replaced.

The PK data from the additional participants enrolled in Cohort 1C-2 will replace the uninterpretable PK data from Cohort 1C; however, the safety data from both Cohorts 1C and 1C-2 will be analyzed and included in the clinical study report.

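### Dose proportionality: raw-scale least squares widens the CI for b about 1.75-fold against a log-log fit, and a CI that merely includes 1 counts as support for linearity

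*Combined protocol and SAP*

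**What the plan says.** Section 11.2.6 relates Cmax and the AUCs to dose through P = a × Dose^b; the relationships of these parameters "and dose for both phases will be assessed using the power model". On fitting it says: "The power model will be fit to the individual subject data using nonlinear least squares regression", naming SAS PROC NLIN or an equivalent. It mentions no log transform, weights or error model.

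The decision rule has two parts. The estimate of b should be about 1, for which no numerical bound is given, and it should come "with a 95% confidence interval that includes 1 indicates linearity or dose proportionality".

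Elsewhere the plan works on the log scale. The statistical paragraph of the Synopsis asks for geometric means and geometric CVs of PK data, and the food-effect analysis in Section 11.2.6 estimates geometric mean ratios.

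On the data: "Part 1 will include single-ascending doses of CC-42344 100 mg, 200 mg, 400 mg, and 800 mg" (Synopsis), with 6 active subjects per cohort (Section 6.1). At 400 mg, "The PK data from the additional participants enrolled in Cohort 1C-2 will replace the uninterpretable PK data from Cohort 1C" (Section 7.2.3), and Cohort 1C-2 also has 6 participants. On sampling, Section 2.1, footnote 9, has all Part 1 cohorts sampled to 48 h and adds: "Additional samples to be collected at 72 and 96 hours postdose for Cohorts 1C and 1D". Section 11.1 gives no formal basis for the sample size.

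**The concern.** If exposure varies by a roughly constant percentage, its standard deviation grows with dose: at b = 1 the raw SD at 800 mg is 8 times that at 100 mg. Least squares on untransformed values acts as if the SD were the same at every dose. The top dose then dominates the fit, and information from the lower doses is largely wasted.

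The decision rule adds to this. Failing to exclude b = 1 counts in favour of proportionality, so a noisier fit meets the CI condition more easily. An inefficient estimator combined with such a rule can let a real departure be reported as linear. For scale, b = 1.2 over an 8-fold dose range means a dose-normalised exposure 8^0.2 = 1.52 times as high at 800 mg as at 100 mg.

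A smaller matter is that the power model covers AUC(0-t), while later samples are scheduled only at the two higher doses. The observation horizon can therefore rise with dose and push b upward.

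**Working it through.** The plan states no precision or power for b, so there is no figure of its own to reproduce.

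**Inputs.** From the documents: doses 100, 200, 400 and 800 mg, 6 active subjects each (24 in the fit), two-sided 95% CI. Assumed, because the documents give no planning value: log-normal variation with a constant CV of 20–40%. The raw-scale fit is taken as unweighted, which is how the silence on weights reads.

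**1. Where the raw fit gets its information.** With b = 1, the expected residual sum of squares by dose is proportional to dose², that is 1 : 4 : 16 : 64 (sum 85). The shares are about 1%, 5%, 19% and 75%.

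**2. SD of b, log-log fit.** Sxx = 6 × (ln 2)² × (1.5² + 0.5² + 0.5² + 1.5²) = 6 × 0.4805 × 5 = 14.41. At CV 40%, s = √ln(1 + 0.4²) = 0.385, so SD(b) = 0.385/√14.41 = 0.10. With t(22 df) = 2.074 the half-width is 0.21.

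**3. SD of b, raw fit (b = 1, large-sample approximation).** Let x = 0, 1, 2, 3 be log dose in units of ln 2 and w = dose² = 1, 4, 16, 64. The weighted mean of x is 228/85 = 2.682. Then Σw(x − 2.682)² = 32.4 and Σw²(x − 2.682)² = 585. SD(b) ≈ CV × √(585/6) / (32.4 × ln 2) = 0.44 × CV, or 0.18 at CV 40%, and 2.074 × 0.176 gives a half-width of 0.37.

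**4. Simulation.** Wald t intervals on 22 df, at least 2,000 runs per cell (Monte Carlo standard error at most about 1 percentage point). At CV 40% and b = 1 the mean half-width is 0.37 raw against 0.21 log-log, a ratio of 0.37/0.21 = 1.76. Median half-widths at CV 20/30/40% are 0.180/0.269/0.347 against 0.106/0.158/0.207, a ratio of about 1.7. As a highest-to-lowest dose-normalised ratio around 1, ±0.37 means 8^±0.37 = 0.46 to 2.16, and ±0.21 means 8^±0.21 = 0.65 to 1.55.

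| True b | Condition met | CV 30%: raw | CV 30%: log-log | CV 40%: raw | CV 40%: log-log |
|---|---|---|---|---|---|
| 1.2 | CI includes 1 | 82% | 30% | 91% | 54% |
| 1.2 | CI includes 1 and b within 1 ± 0.2 | 51% | 30% | 52% | 46% |
| 1.0 | CI includes 1 and b within 1 ± 0.2 | 86% | 95% | 76% | 94% |

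The loss is smaller below 1: at b = 0.8 and CV 40% the CI alone includes 1 in 69% of trials (raw) against 53% (log-log). Coverage of the raw-scale interval is about 94–96%.

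**5. Would equivalence limits work instead?** Limits of 0.80–1.25 on the dose-normalised ratio translate to 1 ± ln 1.25/ln 8 = 0.893 to 1.107 for b. Using a 90% CI from the log-log fit, a truly proportional drug passes in 29% of trials at CV 20%, about 1% at CV 30% and about 0% at CV 40%.

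**6. AUC(0-t) horizon.** Under exact proportionality, let a fraction f of AUC lie in a terminal phase with rate constant k. Adding ln[(1 − f·e^(−96k))/(1 − f·e^(−48k))] at 400 and 800 mg and regressing on ln dose shifts b by +0.02 to +0.06 for a 15 h half-life (f = 30–100%) and +0.03 to +0.13 for 24 h. The half-lives are assumed.

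**The case against.** The strongest reply is that the rule is not a bare CI check. A reader might infer that proportionality is declared whenever the CI includes 1, and that marked non-proportionality is usually called linear. The text does not support that, because b must also be about 1. Reading this as ±0.2 brings the rate for b = 1.2 down to about half and holds every case tried at b = 0.75 or 1.25 below 50%. This stands. Two limits apply. The bound is unstated, so it could be settled after the data are seen. And even with ±0.2 the raw fit does worse both ways: at b = 1.25 it passes 37% against 13% (CV 30%) and 42% against 29% (CV 40%), while it passes a proportional drug less often. The near 50% at b = 1.2 partly reflects a truth lying exactly on the assumed bound.

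The frequencies also depend on a CV that the documents do not give. At CV 20% the CI condition alone passes b = 1.25 in 42% and b = 0.75 in 14% of trials. At b = 0.5 it passes 0–40% across CVs of 20–80%. That the fit is unweighted is an inference from silence.

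A reader might also suppose that the linearity finding is used to extrapolate exposure to untested regimens. Nothing in the documents says so. Section 6.2 bases its 200 mg projection on the observed 200 mg cohort and an assumed accumulation, Section 9.4 bases escalation on committee review, and dose proportionality is not a listed endpoint in Section 5. Nor does Section 11.2.6 pool Parts 1 and 2 in one fit; it compares the phases descriptively.

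The horizon effect is small beside a half-width of 0.37. It arises only if the late samples are quantifiable, and AUC(inf) is modelled too. Its upper end needs all AUC in a 24 h phase, implying 1/(1 − 0.5) = 2-fold accumulation on daily dosing, whereas Section 6.2 reports no significant accumulation up to 200 mg.

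**Conclusion.** The concern holds as one of efficiency and interpretation. Under an assumed constant log-normal CV of 20–40%, with 6 active subjects per dose over 100–800 mg and no weighting, the planned fit gives a CI for b about 1.75 times as wide as a log-log fit of the same data when b = 1. The interval is valid. The flaw is the lost precision, together with a rule that takes failure to exclude 1 as support for proportionality and leaves about 1 undefined. The half-width ratio is stable over the CVs tried; the misclassification rates vary with CV, with the true b and with the bound chosen. The AUC(0-t) horizon is a secondary matter, clear in direction and probably small. This is a descriptive PK analysis and no stated trial decision depends on it, but the improvement costs almost nothing.

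**What to change.** In Section 11.2.6, replace the nonlinear fit with linear regression of ln(P) = ln(a) + b × ln(Dose). State that it is run separately for the Part 1 fasted data and for Part 2 by day, since Section 8.4 doses Part 2 after food.

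Report b with its 95% CI and the implied dose-normalised ratio of highest to lowest dose (r^(b−1), where r is the dose range) as estimates. Say explicitly that a CI including 1 is not proof of proportionality. Equivalence limits such as 0.893–1.107 should not serve as the verdict rule at this sample size, because even a proportional drug would almost never meet them at CV 30% or more.

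As a secondary change, use AUC(inf) where estimable, or a common-horizon AUC(0-48), in place of AUC(0-t) in the Part 1 fit.

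The cost is one paragraph and a simpler program, with no new data. The downside is that the result will often be an imprecise estimate and not a declaration of linearity.
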